Visit 2. Subjects will be assessed again 4 weeks after their home therapy program. At this visit they will also receive baseline testing and training on the device. After this visit, subjects will receive the device for training at home, which will be monitored on a weekly basis remotely by the occupational therapist to ensure compliance and to answer any questions.

Visit 3. This will be the post-device treatment assessment visit.

VI. Data Analysis & Data Monitoring

Data Analysis

Aim 1: Introduce home-based targeted upper limb training in children with hemiplegia from ABI using a bimanual-to-unimanual training approach. We will test the hypothesis that child-friendly home-based upper limb bimanual-to-unimanual training will lead to greater compliance and improved motor outcome on the Fugl-Meyer Scale, the Assisting Hand Assessment Test, active Range of Motion assessments, the Melbourne Assessment 2 and the PedsQL, compared to the conventional home training program. The groups will be compared using a two-way ANOVA.

Aim 2: Improve the understanding of the pattern of recovery of isolated joint movements in the pediatric population with hemiplegia following ABI. We will test the hypothesis that individuals receiving device-based bimanual-to-unimanual training will show improvement in active range of motion across upper limb joints compared with a conventional home training program.

The results of this study will pave the way for both understanding and meeting the needs of pediatric patients with Acquired Brain Injury in a systematic manner. Given the extent of plasticity in children there is a great need to rapidly optimize recovery so that physical, emotional and intellectual growth are as unhindered as possible. There is currently a dearth of evidence in how this can be accomplished. This study will provide pilot data for a larger study to optimize motor outcome pertaining to upper limb recovery as rapidly as possible.

Data Monitoring

The PI will be overall responsible for data monitoring.

(1) Types of Data or Events: All accumulated outcome data, enrollment numbers, reportable event data (including adverse reactions and unanticipated problems) and the overall compliance with the protocol will be monitored.

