Data Stored for Future use: The data collected will be used as pilot data to plan future studies. New questions may come up from this study that may be addressed by reanalyzing the collected data. The data will be stored for up to 7 years. The data will be labeled, stored, and accessible to the PI and delegates as described in the section: Data Storage and Confidentiality. If patients specifically request to withdraw their data from the data stored for future use, they must do so in writing, which will be kept on file. Their data will be segregated from the rest of the data and not used for future analysis. However it will be stored for analysis of the present study and as per rules of publication, for at least 7 years post- publication.

VIII. Safety and Adverse Events

RISK/BENEFIT ASSESSMENT

Risks: The risk of injury from the BAT is minimal as it is a non-powered, non-robotic device and all movements are controlled by the patient. However training may lead to muscle soreness in the unaffected and affected arms. There is a risk of fatigue in patients with stroke who may have weakness. There is a risk of breach of confidentiality since subjects will be answering questionnaires.

Protection against Risks: Fatigue in patients with stroke will be minimized by setting the training duration to short periods tolerated by the patient initially and then increasing it gradually, to build endurance. The subjects will be told that they can take rest periods as often as needed. The speed of training will be controlled by the subject.

Potential Benefits to the Subjects: The subject's participation may provide valuable information that will help in the development of effective tele-rehabilitation. This information may help us to improve the way we treat future stroke subjects

IX. Subject Identification, Recruitment, Consent/Assent

1. Method of Subject Identification and Recruitment

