- 3. Subject Capacity.** The subjects recruited for this study will be community-dwelling individuals with capacity to provide consent and assent. The parents will provide consent for minors (5-17) via a separate consent form.
- 4. Subject /Representative Comprehension.** Capacity will be determined by a general conversation between the subject/ authorized representative and the PI to assess the subject's verbal understanding of the protocol including the nature and purpose of the study, the procedures involved, as well as the risks and benefits of participating versus not participating; appreciation of the significance of the disclosed information and the potential risks and benefits for one's own situation and condition; and the ability to engage in a reasoning process about the risks and benefits of participating versus alternatives, and; the ability to express a choice about whether or not to participate.
- 5. Subject Withdrawal.** Subjects may decide not to participate in the research study at any given time without any penalty. Withdrawal can be made by informing the research study staff; including the PI; verbally or in writing. Upon withdrawal, subject's data will be removed from the study research data immediately.
- 6. Debriefing Procedures.** No information will be purposely withheld from subjects.
- 7. Consent Forms.** The IRB Standard Consent Forms and Assent form will be used (please see attached).
- 8. Documentation of Consent.** The study and the consent form will be thoroughly discussed with each subject, section by section. Subjects will be asked to provide a statement of their understanding of the procedures, risks, and general concept of the study. The consent document, and documentation of the process, will be stored in the PI's office at the Rusk Institute of Rehabilitation Medicine, NYU Medical Center, on a password protected computer and/or in a locked filing cabinet. The computer will be in a locked, fixed location (no mobile laptop), password protected, and on a local network.
- 9. Costs to the Subject.** Subjects will not incur any costs for participating in the study.
- 10. Payment for Participation.** There will be no compensation for participation in this study.

X. Conflict of Interest

Conflict of Interest

[name] (Co-I) is the inventor of the device and she has disclosed her conflict of interest with CIMU.

XI. Investigators' qualifications and experience (CVs attached)

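### Deleting all data of a child who withdraws (Section IX.5) leaves the compliance, motor and final safety summaries describing only the children who stayed

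*Combined protocol and SAP*

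**What the plan says.** Section IX, item 5 (IX.5 below) sets the rule: on withdrawal, the child's "data will be removed from the study research data immediately". The trigger is light: "Withdrawal can be made by informing the research study staff; including the PI; verbally or in writing". The item makes no exception for any kind of data already collected, and no other section adds one.

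Section VII (Data Stored for Future Use) deals with a different request: "If patients specifically request to withdraw their data from the data stored for future use, they must do so in writing". Those data are set apart from later re-use, but the section continues: "However it will be stored for analysis of the present study and as per rules of publication, for at least 7 years post- publication".

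Section VI (Data Analysis) makes compliance part of the Aim 1 hypothesis. Device training "will lead to greater compliance and improved motor outcome on the Fugl-Meyer Scale" and the other scales, compared with conventional home training. The stated method is a two-way ANOVA. No analysis population or missing-data rule is given. Under Data Monitoring, item 1, the same section says that "reportable event data (including adverse reactions and unanticipated problems) and the overall compliance with the protocol will be monitored", along with outcome data and enrollment counts.

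Section II has all 20 children do 4 weeks of conventional training and then 4 weeks of device training. Section IV.2 drops children who are consistently below 80% compliance and does not say what happens to their data.

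**The concern.** In a feasibility study, withdrawal is itself a result. It is the most extreme form of non-compliance, and the children who withdraw are likely to include those who found the training burdensome or who had the soreness or fatigue that Section VIII lists as risks. Deleting their records removes the least favourable observations from an outcome that Aim 1 sets out to test.

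The sequential design widens the loss. A child who withdraws in weeks 5 to 8 has already given a baseline assessment, a full conventional-period log and a Visit 2 assessment. All of it goes, although it is complete and unaffected by the later decision.

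At stake are the planning inputs that this pilot is meant to supply. Section II says that its data will be used to size future studies, and Section 1.2 that they will support a grant application. Compliance and attrition taken from a file without withdrawers would mislead that planning.

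**Working it through.** The plan states no dropout rate, power or expected compliance, so it has no figure to reproduce. The check has two parts.

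**1. The rules side by side**

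| Route | Trigger | Fate of data in the present analysis |
|---|---|---|
| IX.5 | Family tells staff, verbally or in writing, that they withdraw | Removed at once |
| VII | Family objects in writing to future use | Kept |
| IV.2 | Study drops a child below 80% compliance | Not stated |

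The triggers differ, so IX.5 and VII can both be followed. They are uneven, however: an explicit objection to re-use leaves the data in the present analysis, while a verbal withdrawal, which need say nothing about data, erases them.

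**2. Illustration of size for mean compliance**

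From the documents: N = 20. Assumed: stayers average 90%; withdrawers average c = 30% or 50% of scheduled sessions; w = 2, 4 or 6 children withdraw.

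All-enrolled mean = [(20 − w) × 0.90 + w × c] / 20.

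| w | c = 30% | c = 50% | Retained file | Overstatement |
|---|---|---|---|---|
| 2 | (16.2 + 0.6)/20 = 84% | (16.2 + 1.0)/20 = 86% | 90% | 4-6 points |
| 4 | (14.4 + 1.2)/20 = 78% | (14.4 + 2.0)/20 = 82% | 90% | 8-12 points |
| 6 | (12.6 + 1.8)/20 = 72% | (12.6 + 3.0)/20 = 78% | 90% | 12-18 points |

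What the assumed 30-50% means: five sessions a week for 4 weeks is 20 sessions per period, or 40 in all. A child who completes every conventional session and withdraws as device training starts has 20/40 = 50%. A child who stops after 12 sessions has 12/40 = 30%.

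Retention with w = 4 is 16/20 = 80% (exact 95% CI 56-94%). The retained file alone holds 16 records, all from children who stayed.

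**The case against.** Several objections have force, and each limits the point.

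- **Section VII.** A reader might infer that it contradicts IX.5, or already provides for keeping a withdrawer's data. It does neither. It covers only a written objection to future use and is silent on withdrawal from participation. What remains is the unevenness shown above.
- **Stopping training.** A reader might infer that any child who stops training is erased. IX.5 applies when staff are told of a withdrawal. A child who simply stops falls under Section IV.2, where the fate of the data is not stated. Some of the assumed low compliers might leave by that route, so the illustrated loss cannot all be charged to IX.5. How many depends partly on the denominator: the 50% child above was fully compliant until withdrawal, so IV.2 would not have caught that child earlier.
- **Safety.** A reader might infer that safety signals are concealed. Section VI has adverse events compiled by the PI as they occur and reportable events sent to the IRB within 5 business days, and nothing says that IX.5 erases those reports. The loss is to the study dataset and the final tabulations.
- **Retention.** Enrollment numbers are monitored, so 16/20 could probably be recovered. No text says that retention would be reported on the remaining records only.
- **The contrast.** The illustration concerns absolute compliance, whereas Aim 1 compares two periods within the same children. A child who leaves before device training could not supply that within-child contrast under any rule.
- **Family rights.** Deletion on withdrawal is a commitment to families in a paediatric study. Changing it is more than an analytical matter, and the consent form is not available to check.

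None of these supplies an exception to IX.5, and none returns a withdrawer's assessments, logs or non-reportable events to the dataset.

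**Conclusion.** The point holds in a limited form. IX.5 is an unqualified rule and, followed as written, it restricts the compliance, motor and final safety summaries to children who stayed, including for a conventional period that a child has completed. On the assumed inputs, mean compliance is overstated by 4 to 18 points for 2 to 6 withdrawals among 20. Each of those inputs is an assumption, and part of the effect may arise through Section IV.2 instead. The bias in the device-versus-conventional contrast is likely, because children who leave in the device period lose both periods, but the documents give nothing from which to derive its size. The change is cheap and worth making before a child withdraws, since data once deleted cannot be brought back.

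**What to change.** Rewrite IX.5 so that withdrawal ends further data collection, while outcomes, training logs and adverse events already collected are kept for the present analysis unless the family asks for deletion. Then:

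- Report the number of withdrawals, with timing and period, and the number of deletions requested.
- State that the same data-retention rule applies to children dropped under Section IV.2. This concerns their data only, not the drop rule itself.
- Use all enrolled children as the denominator for compliance and retention.
- Include every available visit in the outcome analysis, with a method that accepts children who lack Visit 3, such as a mixed model for repeated measures.

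Cost: a few sentences in IX.5, IV.2 and VI, and no added visits. The consent and assent forms need matching wording and IRB approval, and the new rule applies to children consented under it. Reported compliance and retention may be less favourable.
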